10.5.4 Visits 11-17 (Weeks 4, 5, 6 and 7 ± 2 days)

Refer to Table 2 Summary of Schedule of Events: Baseline to Week 12				
Visits 11-17	Weeks 4, 5, 6, 7 ± 2 days	Follow-up	Home nurse visits	Cross-reference
Vital signs				Section 8.1.4
Local Laboratory: Liver biochemistry panel (twice per week)				Section 8.1.12
Sirolimus				Section 7.5
Oral steroid (Prednisone or Prednisolone)				Section 7.5.1
Adverse events				Section 9.2
Concomitant medications				Section 8.1.2
Visit 16, Week 6: A call or a video consultation between Investigator and patient (check for patient health and for the occurrence of any adverse event since the last visit)				

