6.3 Stopping Rules

Any of the following occurrences will result in pause of further dosing (including escalation to a higher dose level) while the events are under investigation:

- Any death during the study period;
- Any patient develops Grade 3-4 (CTCAE) toxicity;
- Any patient develops copper deficiency (Section 9.7);
- Any occurrence of a newly diagnosed malignancy at any point after vector infusion;
- Neurological, psychiatric or behavior-related adverse event (either new or worsening from baseline) suggestive of IMP-induced deterioration (possibly, probably or definitely related), per Investigator judgment;
- Dose limiting toxicity (DLT), as per DLT definition below;
- Two cases of DILI, as defined below, irrespective of causality.

Definition of DILI criteria:

- a. For patients with baseline AST and ALT values \leq ULN: ALT or AST \geq 3x ULN and Total Bilirubin \geq 2x ULN;
For Patients with baseline AST or ALT values $>$ ULN: AST or ALT $>$ 2x baseline and \geq 3x ULN] and Total Bilirubin \geq 2x ULN.
- b. ALP \geq 2x ULN and Total Bilirubin \geq 2x ULN;
- c. For patients with Gilbert's syndrome: ALP \geq 2x ULN and Direct Bilirubin \geq 2x ULN;
- d. ALT or AST \geq 3x ULN and INR \geq 1.5;
- e. ALP \geq 2x ULN and Direct Bilirubin or Total Bilirubin \geq 2x ULN and INR \geq 1.5;
- f. ALT or AST \geq 5x ULN; or

Protocol VTX-801_CLN_001	Investigational Product: VTX-801
	Version: 9 dated 07 AUG 2023
	Author: Aixial Group CRO

g. Hepatic decompensation.

In the event a patient meets any of these DILI triggers, a search for causality should be conducted (as per current guidelines: Clinical Practice Guidelines: Drug-induced liver injury, [EASL, 2019](#) and Guidance for Industry Drug-Induced Liver Injury: Premarketing Clinical Evaluation, [FDA guideline, 2009](#)), the corresponding suspected DILI forms should be completed and the event reported (see Section [9.6](#)). Testing of liver biochemistry should be repeated within 48 to 72 hours to confirm the abnormalities and the patient should be placed in close monitoring and followed until they normalize or stabilize.

If two patients experience serious liver injury (as defined by above thresholds) or a hepatic decompensation event, the trial should be paused, and the DMC should conduct a review and provide supplemental causality assessment. If the DILIs are deemed to be related to VTX-801, then the study will remain on hold and further study continuation should be discussed with FDA.

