7.5.2.2 Reporting, management and search for etiology of transaminase increase

In case an ALT increase $\geq 1.5 \times$ baseline is observed between Week 2 and Month 9 post-VTX-801 administration, and **within 24 hours of awareness**, the Investigator will enter the AE into the eCRF and discuss with the Sponsor medical monitor (or delegate) the appropriateness of initiating reactive steroid treatment.

If the above-mentioned transaminase increase is ALT or AST $\geq 5 \times$ ULN (consistent with suspected DILI criteria listed in Section 6.3), a DILI form will be completed and reported as outlined in Section 9.6. A liver biopsy will be performed as soon as possible (if possible, within 24-48 hours), in order to assess the results of the liver biopsy and the respective transaminase elevation for causality through HAC adjudication; furthermore, testing of liver biochemistry should be repeated within 48 to 72 hours to confirm the abnormalities and the patient should be placed in close monitoring and followed until normalization or stabilization. *Note that DILIs will be evaluated as per current guidelines: Clinical Practice Guidelines: Drug-induced liver injury, EASL, 2019 and Guidance for Industry Drug-Induced Liver Injury: Premarketing Clinical Evaluation, FDA guideline, 2009.*

If the decision is taken to initiate reactive steroid treatment:

- An unscheduled sampling for IFN-gamma ELISpot to AAV3B capsid and miniATP7B transgene assays will be taken, ideally before steroid reactive treatment initiation.

Protocol VTX-801_CLN_001	Investigational Product: VTX-801
	Version: 9 dated 07 AUG 2023
	Author: Aixial Group CRO

- The investigator will perform the evaluation for an alternative etiology for liver disease (other than T-cell immune response to VTX-801), including:
 - o acute viral hepatitis (immediate testing):
 - PCR for HSV, CMV, EBV, HCV
 - serology for HAV: HAV IgM
 - HBV testing: HBsAg and if positive HBV DNA
 - serology for HEV (IgG and IgM) and HEV RNA
 - o alcoholic and autoimmune hepatitis: ANA, SMA, and anti-LKM1 auto-antibodies, as well as total IgG testing,
 - o hepatobiliary disorders other than WD,
 - o cardiovascular causes,
 - o concomitant treatments.

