8.1.12 Local Laboratory Standard and Special Evaluations

The parameters listed in [Table 9](#) will be analyzed by the Local Laboratories. Please refer to [Table 8](#) for full sampling frequency and to the Schedule of Events ([Table 2](#), [Table 3](#)) for the related time points.

Protocol VTX-801_CLN_001	Investigational Product: VTX-801
	Version: 9 dated 07 AUG 2023
	Author: Aixial Group CRO

Table 10 Standard and Special Parameters to be Analyzed by the Local Laboratory

Liver Biochemistry Panel ^a	Others

 • ALT • AST • GGT • LDH • Total bilirubin • Direct bilirubin (DB) • ALP 	
 • Urine pregnancy test • Tuberculosis tests (QuantiFERON®-TB Gold) • Urine drug test screen (amphetamines, cocaine, opiates, phencyclidine (PCP)) 
Special investigations (refer to Section 7.2.5)
 
 • Cytokines (including at least IL-6) • Complement 
Special investigations (refer to Section 9.7)
 
 • Blood smear with corrected reticulocyte count 
Special investigations (refer to Section 7.5.2)
 
 • PCR for HSV, CMV, EBV, HCV • Serology for HAV IgM • HBsAg and if positive HBV DNA • Serology for HEV (IgG and IgM) and HEV RNA • Autoimmune hepatitis: ANA, SMA, anti-LKM1 auto-antibodies, total IgG

a. Liver biochemistry panel will be performed by both Local and Central Laboratories. The local results will primarily be used by the site to guide decisions by the treating physician to ensure patient safety; the central results will be used for the statistical analysis. Both sets of data will be captured in the EDC (Electronic Data Capture) system.

Abbreviations: ALP= ALkaline Phosphatase; ALT= ALanine aminoTransferase; ANA= AntiNuclear Antibodies; AST= ASpartate aminoTransferase; CMV= CytoMegaloVirus; DB= Direct Bilirubin; DNA= DeoxyriboNucleic Acid;

EBV= Epstein-Barr Virus; EDC= Electronic Data Capture; GGT= Gamma-Glutamyl Transpeptidase; HAV= Hepatitis A Virus; HBV= Hepatitis B Virus; HCV= Hepatitis C virus; HEV= Hepatitis E Virus; HSV= Herpes Simplex Virus; IgG= Immunoglobulin G; IgM= Immunoglobulin M; IL-6= Interleukin-6; LDH= Lactate DeHydrogenase; LKM1= Liver-Kidney Microsome Type 1; PCP= Phencyclidine; PCR= Polymerase Chain Reaction; RNA= RiboNucleic acid; SMA= Smooth Muscle Antibodies.

Protocol VTX-801_CLN_001	Investigational Product: VTX-801
	Version: 9 dated 07 AUG 2023

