10.5 Visits 8-46: Follow-up Until End of Year 1 Post-VTX-801 Administration

10.5.1 Visit 8 (Day 8 ± 2 days)

Refer to Table 2 Summary of Schedule of Events: Baseline to Week 12				
Visit 8	D8 ± 2 days	Follow-up	Outpatient visit	Cross-reference
Vital signs				Section 8.1.4
Physical examination				Section 8.1.3
Alcohol consumption				Section 7.7
Central Laboratory: Hematology				Section 8.1.11
Central Laboratory: Liver biochemistry panel				Section 8.1.11
Local laboratory: Liver biochemistry panel				Section 8.1.12
Vector shedding: blood, urine, saliva, feces - mandatory Note: at all visits until end of year 1, as applicable, vector shedding sampling is to occur at every site scheduled visit until 3 consecutive concerned samples are negative (at or below quantification limit)				Section 8.2.3
Sirolimus				Section 7.5
Sirolimus level test: sampling for blood trough concentration after 7 to 14 days according to local practice				Section 7.5
Oral steroid (Prednisone or Prednisolone)				Section 7.5.1
Adverse events				Section 9.2
Concomitant medications				Section 8.1.2

Protocol VTX-801_CLN_001	Investigational Product: VTX-801
	Version: 9 dated 07 AUG 2023
	Author: Aixial Group CRO

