17.1.2 Baseline (V2) to Week 12 (V29)

Table 18 Blood Sample Volumes from Baseline (V2) to Week 12 (V29)

Assessment	Blood Volume (mL)															Total Volume (mL)	
	V2 D-7	V3 D-3	V4 D-2	V5 D-1	V6 D1	V7 D2	V8 W2	V9 W3	V10 W4	V11-17 W4-7	V18 W8	V19-25 W8-11	V 26 W12	V27 W12	V28 W12	V29 W12	
Pregnancy test	2	-	-	-	-	-	-	-	-	-	-	-	-	-	-	2	
Blood biochemistry (with lipid panel at Week 4) and hematology, coagulation	16	-	-	-	-	-	16	-	16	-	-	-	16	-	-	64	
Lipid panel											5					5	
Central Laboratory: Liver biochemistry panel	5	-	-	-	-	-	5	-	5	-	5	-	5	-	-	25	
Local Laboratory: Liver biochemistry panel	5	-	-	-	-	5	5	5	5	5 per visit	5	5 per visit	5	-	-	5	110
Sirolimus level test	-	3	-	-	-	-	3	-	3	-	3	-	-	-	-	12	
Ceruloplasmin CuEXC	7	-	-	-	-	-	-	-	7	-	-	-	7	-	-	21	
Total Cu																	
Total Cu Ceruloplasmin bound Cu (Cp-Cu ANCC)	12	-	-	-	-	-	-	-	12	-	-	-	12	-	-	36	
Anti-AAV3B capsid neutralizing antibodies	-	-	-	-	4	-	-	-	4	-	-	-	-	-	-	8	
Vector shedding: blood	-	-	-	1	-	1	1	-	1	-	1	-	1	-	-	1	
ELISA: anti-AAV3B capsid and miniATP7B antibodies	4	-	-	-	-	-	-	-	4	-	4	-	4	-	-	16	

Protocol VTX-801_CLN_001	Investigational Product: VTX-801
	Version: 9 dated 07 AUG 2023
	Author: Aixial Group CRO

Assessment	Blood Volume (mL)															Total Volume (mL)	
	V2 D-7	V3 D-3	V4 D-2	V5 D-1	V6 D1	V7 D2	V8 W2	V9 W3	V10 W4	V11-17 W4-7	V18 W8	V19-25 W8-11	V 26 W12	V27 W12	V28 W12	V29 W12	
ELISpot: AAV3B capsid and miniATP7B	50	-	-	-	-	-	-	-	50	-	50	-	50	-	-	-	200
Total volume per column	101	33	20	21	24	6	30	5	107	35	73	35	130	20	20	26	686

Abbreviations: AAV3B= Adeno-Associated Virus serotype 3B; ANCC= Accurate Non-Ceruloplasmin-bound Cu; ATP7B= Copper-transporting P-type ATPase; Cp-Cu= Ceruloplasmin-bound copper; Cu= Copper CuEXC= Exchangeable Copper; D= Day; ELISA= Enzyme-Linked immunosorbent Assay; ELISpot= Enzyme-linked ImmunoSpot; [REDACTED]; V=Visit D=Day W=Week

Protocol VTX-801_CLN_001	Investigational Product: VTX-801
	Version: 9 dated 07 AUG 2023
	Author: Aixial Group CRO

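### DILI criterion (d) needs an INR that the liver panel does not contain and Section 10 lists at only 5 of 32 Year-1 panel visits; the Visit 8 blood tests also conflict with Table 18

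*Protocol*

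**What the plan says.** **Stopping rule.** The events in Protocol 6.3 that pause dosing include "Two cases of DILI, as defined below, irrespective of causality". Two of the criteria (a) to (g) need an INR of at least 1.5. Criterion (d) pairs it with ALT or AST at least 3x ULN. Criterion (e) pairs it with ALP and direct or total bilirubin, each at least 2x ULN. Criteria (a), (b), (c) and (f) use only transaminases, ALP and bilirubin; (g) is hepatic decompensation.

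**Panel.** In Table 8 (central) and Table 10 (local) the liver biochemistry panel is ALT, AST, GGT, LDH, total and direct bilirubin, and ALP. INR appears only under Coagulation in Table 8. The footnote to Table 10 says: "The local results will primarily be used by the site to guide decisions by the treating physician to ensure patient safety".

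**Schedule.** The laboratory line for the home-nurse visits in Section 10.5.4 is "Local Laboratory: Liver biochemistry panel (twice per week"; Section 10.5.6 has the same. After dosing in Year 1, Section 10 lists coagulation at Visits 10, 26, 36, 39 and 46.

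**After a raised result.** Section 7.5.2.2 says "testing of liver biochemistry should be repeated within 48 to 72 hours to confirm the abnormalities", and 6.3 has the same repeat. Neither names INR, and nor does the etiology work-up.

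**Visit 8.** Section 10.5.1 lists "Central Laboratory: Hematology" and the central and local liver panels. Table 18 puts 16 mL at Visit 8 in its row "Blood biochemistry (with lipid panel at Week 4) and hematology, coagulation".

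**SAP.** Section 7.9.1 identifies liver adverse events from the suspected-DILI question on the eCRF adverse event page. It does not derive them from laboratory values.

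**The concern.** A criterion that counts towards a stopping rule should be measurable when the event is expected. Protocol 2.5.1 and 4.4 both say that most transaminase rises after AAV dosing fall in the first 12 weeks. That is when sampling is densest and when INR is almost absent from it.

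If no INR is drawn, a patient who meets the transaminase half of (d) cannot be classified on the other half. The eCRF question is then likely to be answered No, and the tables cannot tell a patient without DILI from one in whom the criterion was never tested. In a first-in-human trial whose primary endpoint is safety, that distinction matters.

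The Visit 8 conflict is a separate matter. It leaves open whether any biochemistry or coagulation beyond the liver panel is drawn between dosing and Week 4.

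**Working it through.** **1. Reproduce the plan's figures.** Table 18 gives 5 mL per local panel, at V2, V7, V8, V9, V10, V11-17 (7 visits), V18, V19-25 (7 visits), V26 and V29. That is 22 x 5 = 110 mL, as printed. Table 19 has 12 x 5 = 60 mL, as printed. The combined biochemistry, hematology and coagulation row is 4 x 16 = 64 mL in Table 18 and 3 x 16 = 48 mL in Table 19, as printed. The total is 86 + 686 + 316 + 400 = 1,488 mL, as stated in Section 8.3.

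**2. Count post-dose Year-1 panels.**
- From Table 9: Weeks 1-3 give 3; Weeks 4-12 give 9 x 2 = 18; Weeks 13, 15 and 16 give 3; Weeks 20, 24, 28, 32, 36, 40, 44 and 52 give 8. The sum is 32.
- From Section 10: V7-9 (3), V10 (1), V11-17 (7), V18 (1), V19-25 (7), V26 (1), the second Week 12 sample at V28, V29 or V30 (1), V31 (1), V33-35 (3), V36 (1), V37-38 (2), V39 (1), V44-45 (2), V46 (1). The sum is again 32.
- Visit 42, for the expansion cohort only, makes 33. Tables 18 and 19 agree: 22 - 1 baseline + 12 = 33.

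**3. Count those with coagulation listed.**

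| Window | Panels | With INR listed | Share |
|---|---|---|---|
| Year 1, Section 10 text | 32 | 5 | 15.6% |
| Year 1, if Table 18 governs Visit 8 | 32 | 6 | 18.8% |
| Weeks 4-12 | 18 | 2 (V10, V26) | 11% |

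Between V10 and V26 there are 7 + 1 + 7 = 15 consecutive panel visits without INR. They include the on-site Week 8 visit.

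**4. Find the patients who depend on INR.**
- At 5x ULN or more, (f) is met without INR.
- At 3x ULN or more with the bilirubin rise in (a), (a) is met without INR.
- Criterion (d) therefore adds, essentially, ALT or AST from 3x to below 5x ULN without that bilirubin rise and without decompensation.
- Criterion (e) with total bilirubin lies inside (b). With direct bilirubin in Gilbert's syndrome it lies inside (c). What remains is direct bilirubin at least 2x ULN with total bilirubin below 2x ULN in a patient without Gilbert's syndrome.

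**5. Look for a prompt to draw INR in that band.** The repeat in 6.3 follows a DILI trigger already met, and the one in 7.5.2.2 is tied to ALT or AST at least 5x ULN. The etiology work-up follows a decision to start reactive steroids. As written, none of these prompts an INR for a patient between 3x and 5x ULN.

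**6. Effect on the tables.** SAP Section 9 reports 4 patients dosed, 2 in each of two cohorts. One unlabelled case changes a cohort proportion by 1/2 = 50 percentage points and the overall proportion by 1/4 = 25 points.

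**7. Visit 8.** The Table 18 column is 16 + 5 + 5 + 3 + 1 = 30 mL, as printed. In Table 17 hematology alone is 5 mL, and biochemistry with coagulation is 11 mL (5 + 11 = 16). With hematology alone the Visit 8 column would be 5 + 5 + 5 + 3 + 1 = 19 mL. The budget therefore includes 11 mL of tests that Section 10.5.1 does not list.

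**The case against.** **A missed case does not vanish.** A reader might infer that it would drop out of the primary safety tables. The documents do not support that. Under Protocol 7.5.2.2, ALT at least 1.5x baseline between Week 2 and Month 9 is entered as an adverse event, and 9.6 makes it an AESI. It would appear in the SAP's TEAE and AESI rows, and the value would be in the laboratory listing. The DMC also reviews all liver TEAEs (9.2.3). Only the suspected-DILI rows and the DILI count could lose it. An isolated AST rise need not meet the ALT-based AESI, but would still be in the listing. This objection stands.

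**Most of the DILI definition works.** Criteria (a), (b), (c) and (f) run on the panel alone. It would be wrong to read 27 of 32 visits without INR as a rate of missed DILI, because INR matters only when the other half of (d) or (e) is met. This stands too.

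**INR may be drawn anyway.** Sections 7.5.2.1 and 10.11 allow unscheduled sampling, and the work-up list is not exhaustive. The cells and footnotes of Schedule Tables 2 and 3 cannot be seen in the text available. The counts are therefore as listed in Section 10. Permission to sample is still not a stated test.

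**Visit 8.** Table 18 is a volume budget, and Table 8 prints Coagulation inside its Hematology column, so hematology at Visit 8 might be read to include INR. Section 10 names coagulation separately elsewhere, and the Table 18 row also covers biochemistry, so a conflict remains on either reading. Table 18 says nothing about urine, so nothing follows from it about urinalysis.

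**Dosing has ended.** The SAP confirms this, so the effect on the pause rule is now largely historical.

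**Conclusion.** The point holds in a limited form. Criterion (d) is part of the DILI definition behind the two-case pause and the SAP's liver TEAE rows, yet the surveillance panel cannot evaluate it. Section 10 lists INR at 5 of 32 Year-1 panels (6 if Table 18 governs Visit 8; the expansion cohort has 33 panels) and at 2 of 18 in Weeks 4-12. The exposure is essentially one band, ALT or AST from 3x to below 5x ULN without the bilirubin rise in (a) or decompensation. Criterion (e) adds almost nothing.

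The consequence is a possible missing label, not a missing event. With dosing ended, it falls mainly on how DILI is reported in the 4 dosed patients. The documents give no patient results, so nothing here says that a case was missed. The Visit 8 conflict between Section 10.5.1 and Table 18 is real and separate.

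The conclusion assumes that Schedule Tables 2 and 3, which could not be checked, agree with Section 10.

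**What to change.** 1. **Protocol.** The sponsor should reconcile the INR-based criteria in 6.3 with the tests and timing in Tables 8 and 10, 7.5.2.2 and Section 10, so that (d) and (e) can be evaluated. Which tests are drawn, and when, is a clinical decision for the sponsor.
2. **Visit 8.** Reconcile Section 10.5.1, Table 2 and Table 18 so that all three list the same tests.
3. **SAP 7.9.2.** In the laboratory listing, flag each post-dose ALT or AST result at least 3x ULN that meets no other DILI criterion and has no contemporaneous INR as *criterion d not assessable*. State in the SAP what counts as contemporaneous. Apply the flag to local as well as central results, because the home-nurse visits list the local panel. Add a footnote to the liver TEAE tables pointing to the flag.

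The cost is wording changes and one derived flag on data already captured. The flag can be applied to the 4 dosed patients now, and it separates no DILI from not measured.

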10.5.5 Visit 18 (Week 8 ± 2 days)

Refer to Table 2 Summary of Schedule of Events: Baseline to Week 12				
Visit 18	Week 8 ± 2 days	Follow-up	Outpatient visit	Cross-reference
Vital signs				Section 8.1.4

Protocol VTX-801_CLN_001	Investigational Product: VTX-801
	Version: 9 dated 07 AUG 2023
	Author: Aixial Group CRO

Physical examination	Section 8.1.3
Alcohol consumption	Section 7.7
Central Laboratory: Liver and lipid biochemistry panels Fasting conditions are required for the lipid panel.	Section 8.1.11
Local Laboratory: Liver biochemistry panel	Section 8.1.12
Vector shedding: blood, urine, saliva, feces - mandatory Note: at all visits until end of year 1, as applicable, vector shedding sampling is to occur at every site scheduled visit until 3 consecutive concerned samples are negative (at or below quantification limit).	Section 8.2.3
ELISA and IFN-gamma ELISpot	Section 8.2.4
Sirolimus	Section 7.5
Sirolimus level test: sampling for blood trough concentration 8 weeks days after starting treatment with Sirolimus	Section 7.5
Oral steroid (Prednisone or Prednisolone)	Section 7.5.1
Adverse events	Section 9.2
Concomitant medications	Section 8.1.2

10.5.6 Visits 19-25 (Weeks 8, 9, 10 and 11 ± 2 days)

Refer to Table 2 Summary of Schedule of Events: Baseline to Week 12				
Visits 19-25	Weeks 8, 9, 10, 11 ± 2 days	Follow-up	Home nurse visits	Cross-reference
Vital signs				Section 8.1.4
Local Laboratory: Liver biochemistry panel (twice per week)				Section 8.1.12

Protocol VTX-801_CLN_001	Investigational Product: VTX-801
	Version: 9 dated 07 AUG 2023
	Author: Aixial Group CRO

Sirolimus	Section 7.5
[REDACTED]	[REDACTED]
Oral steroid (Prednisone or Prednisolone): last dose at the end of Week 8 unless continued in the case of overt transaminase increase	Section 7.5.1
Adverse events	Section 9.2
Concomitant medications	Section 8.1.2

10.5.7 Visits 26-29 (Week 12)

Only for the expansion cohort: the patient is to be hospitalized, stay at a unit with clinical support or other location approved by the Sponsor [REDACTED]

Refer to Section [10.2](#), Visit 2 for the wash-out instructions for patients on copper chelators or dual chelator and zinc therapy:

Refer to Section [7.6.3](#), for expansion cohort only, [REDACTED]

The 2 samples of Week 12 for “Liver biochemistry panel” will occur at site as much as possible. For example, at Visit 26 collecting the first sample is mandatory, with the second sample collected at Visit 28 or Visit 29.

If the second sample cannot occur at site, it should be collected at the home nurse visit planned after end of hospitalization within Week 12 (Visit 30).

Refer to Table 2 Summary of Schedule of Events: Baseline to Week 12				
Visit 26	Week 12 ± 5 days	Follow-up	In or Out-patient visit	Cross-reference
Vital signs				Section 8.1.4

Protocol VTX-801_CLN_001	Investigational Product: VTX-801
	Version: 9 dated 07 AUG 2023
	Author: Aixial Group CRO

Physical examination	Section 8.1.3
Alcohol consumption	Section 7.7
Urine pregnancy test (for WOCBP only)	Section 8.1.12
Central Laboratory: Blood/urine biochemistry; hematology; coagulation	Section 8.1.11
Central Laboratory: Liver biochemistry panel	Section 8.1.11
Local Laboratory: Liver biochemistry panel (twice per week)	Section 8.1.12
Calculation of MELD, APRI, FIB4 by CRO	Section 8.1.14 Table 11
Ceruloplasmin (enzymatic assay and nephelometry), total Cu, REC, RAC, CuEXC, ANCC	Section 8.1.13
24-hour urinary copper (to end prior to radiocopper administration)	Section 8.1.13
For patients on copper chelator: 
 Patients are to be informed to start the wash-out period without copper-chelator treatment 3 days before radiocopper injection and until the end of the radiocopper investigations. The 24-hour urine copper sample will start 48 hours after initiation of the chelator wash-out period and will end prior to radiocopper administration 	
Vector shedding: blood, urine, saliva, feces Note: at all visits until end of year 1, as applicable but only at this visit during this period of 4 consecutive visits (V26 to V29).	Section 8.2.3
ELISA and IFN-gamma ELISpot	Section 8.2.4
ECG	Section 8.1.5

Protocol VTX-801_CLN_001	Investigational Product: VTX-801
	Version: 9 dated 07 AUG 2023
	Author: Aixial Group CRO

UWDRS, M.I.N.I., SDMT and Stroop Test	Section 8.1.7
[REDACTED]	[REDACTED]
Sirolimus [REDACTED]	Section 7.5
[REDACTED]	[REDACTED]
Adverse events	Section 9.2
Concomitant medications	Section 8.1.2

Refer to Table 2 Summary of Schedule of Events: Baseline to Week 12				
Visit 27	Week 12	Follow-up	In or Out-patient visit	Cross-reference
Vital signs				Section 8.1.4
[REDACTED]				[REDACTED]

Protocol VTX-801_CLN_001	Investigational Product: VTX-801
	Version: 9 dated 07 AUG 2023
	Author: Aixial Group CRO

[REDACTED]	[REDACTED]
Sirolimus [REDACTED]	Section 7.5
[REDACTED]	[REDACTED]
Adverse events	Section 9.2
Concomitant medications	Section 8.1.2

Refer to Table 2 Summary of Schedule of Events: Baseline to Week 12				
Visit 28	Week 12	Follow-up	In or Out-patient visit	Cross-reference
Vital signs				Section 8.1.4
Local Laboratory: Liver biochemistry panel (this could alternatively be taken at Visits 29 or 30)				Section 8.1.12
[REDACTED]				[REDACTED]
Sirolimus administration [REDACTED]				Section 7.5
[REDACTED]				[REDACTED]
Adverse events				Section 9.2
Concomitant medications				Section 8.1.2

Protocol VTX-801_CLN_001	Investigational Product: VTX-801
	Version: 9 dated 07 AUG 2023
	Author: Aixial Group CRO

The patient will leave the hospital after following assessments:

Refer to Table 2 Summary of Schedule of Events: Baseline to Week 12 This visit is for the expansion cohort only.				
Visit 29	Week 12	Follow-up	In or Out-patient visit	Cross-reference
Vital signs				Section 8.1.4
Local Laboratory: Liver biochemistry panel (only if not done at Visit 28)				Section 8.1.12
   				 
   				
Sirolimus administration 				Section 7.5
 				 
Adverse events				Section 9.2
Concomitant medications				Section 8.1.2

Protocol VTX-801_CLN_001	Investigational Product: VTX-801
	Version: 9 dated 07 AUG 2023
	Author: Aixial Group CRO

